5.3.6 Adverse event collection and reporting

AE Collection

The following must be collected and documented on the appropriate eCRF by the Investigator:

- From signing the informed consent onwards through the Residual Effect period (REP), until trial completion, all AEs (serious and non-serious), and all AESIs.

[figure not shown]

Figure 5.3.6:1 AE collection

The REP is defined as 50 days after the last trial medication application. All AEs which occurred through the treatment phase and throughout the REP will be considered as on treatment please see [section 7.3.4](#). Events which occurred after the REP will be considered as post treatment events.

After the last per protocol contact the Investigator does not need to actively monitor patients for AEs. However, if the Investigator becomes aware of SAEs or AESIs that occurred after the last per protocol contact, the SAEs and AESIs should be reported by the Investigator to the Sponsor if considered relevant by the Investigator.

AE reporting to sponsor and timelines

The Investigator must report SAEs, AESIs, and non-serious AEs which are relevant for the reported SAE or AESI, on the BI SAE form via fax immediately (within 24 hours) to the Sponsor's unique entry point (country specific contact details will be provided in the ISF). In specific occasions the Investigator could inform the Sponsor upfront via telephone. This does not replace the requirement to complete and fax the BI SAE form.

For Japan: All SAEs and AESIs must be reported immediately to the head of the trial site. With receipt of any further information to these events, a follow-up SAE form has to be

provided. For follow-up information the same rules and timeline apply as for initial information.

Information required

For each AE, the Investigator should provide the information requested on the appropriate (e)CRF pages and the BI SAE form, e.g. onset, end date, intensity, treatment required, outcome, seriousness, and action taken with the investigational drug(s). The Investigator should determine the causal relationship to the trial medication, and any possible interactions between the investigational drug and a Non-Investigational Medicinal Product.

The following should also be recorded as an (S)AE in the (e)CRF and SAE form (if applicable):

- Worsening of the underlying disease or of other pre-existing conditions

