If a non-flat dose response relationship is established, the significant model(s) from the above candidate set are refitted to the data without any parameter assumptions to generate new estimates of the model parameters from the data. The final model will be obtained via model averaging across the significant models based on Akaike Information Criterion (AIC). The target dose(s) can then be determined from that model by any incorporating information on the minimum clinically relevant effect as well as safety information. The target dose to be chosen should show a benefit of at least 10% in complete renal response rate at week 52 compared to the placebo. This will be measured on the modelled efficacy and only doses within the dose range investigated (0mg-240mg) will be considered although the actual modelling will be performed on a broader range of doses including extrapolation.

If considered necessary and for the purpose of further model refinement, MCPMod might be repeated on the primary endpoint but with an extended set of shapes including the original candidates. Additionally to that covariates may be taken into account in a sensitivity analysis. Finally the approach described by Klingenberg et al ([R15-0407](#)) will be taken into account to show robustness of the primary analysis. Details of these analyses will be described in the TSAP.

Comparisons between treatment groups will be exploratory in nature and based on the numerical comparison of the respective response rates. In addition, unadjusted absolute risk differences of the complete renal response at week 52 between the BI 655064 arms and the placebo group will be analysed. The proportion of responders in each arm, the risk difference

between each arm and placebo and 95% exact confidence intervals will be displayed. Finally, a logistic regression model on the proportion of patients with complete renal response at week 52 with factors treatment and race as strata will be applied. More details on the above analyses as well as additional sensitivity analyses will be given in the TSAP.

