7.3.4 Safety analyses

All treated patients will be included in the safety analysis. In general, safety analyses will be descriptive in nature and will be based on BI standards. No hypothesis testing is planned.

Adverse events will be coded using the Medical Dictionary for Regulatory Activities (MedDRA) coding dictionary. Standard BI summary tables and listings will be produced. All adverse events with an onset between start of treatment and end of the residual effect period (REP), a period of 50 days after the last dose of trial medication, will be assigned to the treatment period for evaluation. Analysis will be performed based on randomised treatment.

Statistical analysis and reporting of adverse events will concentrate on treatment-emergent adverse events. To this end, all adverse events occurring between start of treatment and end of the residual effect period will be considered 'treatment-emergent'. The residual effect period is defined as 50 days. Adverse events that start before first drug intake and deteriorate under treatment will also be considered as 'treatment-emergent'.

Frequency, severity, and causal relationship of adverse events will be tabulated by system organ class and preferred term after coding according to the current version of the Medical Dictionary for Drug Regulatory Activities (MedDRA).

Laboratory data will be analysed both quantitatively as well as qualitatively. The latter will be done via comparison of laboratory data to their reference ranges. Values outside the reference range as well as values defined as clinically relevant will be highlighted in the

listings. Treatment groups will be compared descriptively with regard to distribution parameters as well as with regard to frequency and percentage of patients with abnormal values or clinically relevant abnormal values.

Vital signs, physical examinations, or other safety-relevant data observed at screening, baseline, during the course of the trial and at the end-of-trial evaluation will be assessed with regard to possible changes compared to findings before start of treatment.

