Definition/derivation of CRR for patients who prematurely stop trial medication

The rules below will be applied to derive CRR/PRR/MRR for the ITT:

Proprietary confidential information © 2020 Boehringer Ingelheim International GmbH or one or more of its affiliated companies

- (1) If the reason for discontinuation of treatment is ‘Lack of efficacy’ or AE type is ‘Worsening of disease under study’, then CRR will be defined as ‘Non-responder’.
- (2) If the patient used prohibited meds known to impact CRR following discontinuation of study med, then CRR will be defined as ‘Non-responder’.
- (3) If neither #1 or #2 apply and treatment duration ≥ 46 weeks, then use the lab data collected at Visit 16-EOT/Week 52 to derive the endpoints. If there is no lab data at Visit 16-EOT /Week 52, then use the lab data closest to 52 weeks that is within 6 weeks prior to week 52.
- (4) If neither #1 or #2 apply and treatment duration < 46 weeks, then CRR will be defined as ‘Non-responder’.

Note that patients handled with the above rules are included in the ITT population. They would only be included in the PPS if they complete 46 weeks of the treatment regimen.

For patients who took study drug for < 46 weeks, continued to participate in the trial and have urine collections and serum creatinine determinations, their data will be displayed in a listing.

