7.8.1 Adverse events

AEs will be analysed using BI standards, as described in the guideline, ‘Handling and summarization of adverse event data for clinical trial reports and integrated summaries’ (7).

Unless otherwise specified, the analyses of adverse events will be descriptive in nature. All analyses of AEs will be based on the number of patients with AEs and NOT on the number of AEs.

The analysis of AEs will be based on the concept of treatment emergent AEs. This means that all AEs occurring between first drug intake and end of the residual effect period (REP) will be assigned to the randomised treatment. The residual effect period is defined as 50 days. All AEs occurring before first drug intake will be assigned to ‘Screening’ and all AEs occurring after last drug intake + 50 days will be assigned to ‘Follow-up’ (and presented in listings only). For details on the treatment definition, see [Section 6.1](#)

According to ICH E3 (8), in addition to Deaths and Serious Adverse Events, ‘other significant’ AEs need to be listed in the clinical trial report. These will be any non-serious adverse event that led to an action taken with study drug (e.g. discontinuation or dose reduced or interrupted).

An overall summary of adverse events will be presented. The frequency of patients with adverse events will be summarised by treatment, primary system organ class and preferred term. Separate tables will be provided for patients with adverse events leading to treatment discontinuation, other significant adverse events according to ICH E3 (8), related adverse events and serious adverse events. AEs will also be summarised by maximum RCTC grade.

Proprietary confidential information © 2020 Boehringer Ingelheim International GmbH or one or more of its affiliated companies

Adverse events of special interest (AESI) will be presented in tables and listings for the following:

- Injection site reactions and hypersensitivity, including anaphylaxis reaction
- Malignancies, lymphoproliferative disorders
- Severe infections and opportunistic infections
- Thromboembolism (Thrombosis and adjunct immunosuppression)
- Cytokine release syndrome
- Drug induced liver injury (DILI) (if applicable)

The system organ classes will be sorted by frequency, PTs will be sorted by frequency (within SOC).

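### Lupus worsening stays in the patient-level AE totals, so the SAE, AE-discontinuation and maximum-grade summaries mix lack of efficacy with toxicity and can dilute an effective dose's excess over placebo

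*Protocol*

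**What the plan says.** **Recording.** Protocol 5.3.6 names "Worsening of the underlying disease or of other pre-existing conditions" among the items that should also be recorded as an (S)AE.

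**Counting.** Protocol 7.3.4 treats every adverse event from start of treatment to the end of the 50-day residual effect period as treatment-emergent. SAP 7.8.1 agrees: "all AEs occurring between first drug intake and end of the residual effect period (REP) will be assigned to the randomised treatment". Neither makes an exception for the disease under study. The unit is the patient: "All analyses of AEs will be based on the number of patients with AEs and NOT on the number of AEs".

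**Tables.** SAP 7.8.1 plans an overall summary and a breakdown: "The frequency of patients with adverse events will be summarised by treatment, primary system organ class and preferred term". It continues: "Separate tables will be provided for patients with adverse events leading to treatment discontinuation", with further tables for serious, related and other significant events and a summary by maximum RCTC grade. None is described as excluding lupus worsening. Lupus worsening is also not on the list of events of special interest, so it has no planned line of its own outside the preferred-term rows.

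**The existing flag.** SAP 6.6.1, in the rules for patients who stop trial medication early, uses the AE type "Worsening of disease under study" to set renal response to non-response. The visible text gives it no other use.

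**Use of safety.** Protocol 7.1 and 7.3.1 have the Phase III dose chosen on efficacy and safety, the latter section by "incorporating information on the minimum clinically relevant effect as well as safety information". Protocol 7.3 compares the safety profile of the three active arms with control descriptively.

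**The concern.** A flare can enter the report twice, once as an efficacy failure and once as a unit in the AE totals. It can reach those totals whether the patient stops treatment because of it (Protocol 3.3.4.1) or continues on study drug (Protocol 4.2.1).

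If a dose works partly by preventing flares, placebo collects more of these events. The crude difference between active dose and placebo then falls below the difference in events unrelated to lupus. The error favours the effective dose, in a trial that weighs safety when choosing a dose. The comparison is descriptive, so no model or test separates the two components.

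The preferred-term rows do not repair the totals. If T patients in an arm have any SAE and L of them have a lupus SAE, the number with a non-lupus SAE can be anything from T minus L up to T, because one patient may have both. Maximum grade has the same problem, since a severe flare can set a patient's grade.

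**Working it through.** The plan states no figure for this quantity, so there is nothing to reproduce. What follows is an illustration of size.

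**Inputs**
- Planned arm sizes: 40 on placebo and 40 on 240 mg (Protocol 7.6).
- Planned response: 25% on placebo and 44% on 240 mg (Protocol 7.7, main scenario). Non-response is therefore 75% and 56%, a ratio of 75/56 = 1.34.
- Assumed, because the documents give no rates: non-lupus SAEs t = 10% on placebo and 20% on 240 mg; worsening SAEs w = 5% to 20% on placebo; the two kinds of event independent within a patient.

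**Formula.** Proportion of patients with any SAE = 1 − (1 − t)(1 − w).

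**Case A: worsening in the ratio of planned non-response.** The 240 mg rate is the placebo rate × 56/75.

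| w placebo | total placebo | w 240 mg | total 240 mg | apparent gap |
|---|---|---|---|---|
| 5% | 1 − 0.90×0.95 = 14.5% | 3.7% | 23.0% | +8.5 |
| 10% | 1 − 0.90×0.90 = 19.0% | 7.5% | 26.0% | +7.0 |
| 15% | 1 − 0.90×0.85 = 23.5% | 11.2% | 29.0% | +5.5 |
| 20% | 1 − 0.90×0.80 = 28.0% | 14.9% | 31.9% | +3.9 |

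The true gap is +10 points throughout. At this ratio it disappears when 0.90(1 − w) = 0.80(1 − 0.747w), which gives w = 0.10/0.303, or about 33% on placebo.

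**Case B: worsening held at 5% on 240 mg.** The 240 mg total is 1 − 0.80×0.95 = 24.0%. Against the same placebo totals the gaps are +9.5, +5.0, +0.5 and −4.0 points. In the +9.5 case worsening is equal in both arms, so that half-point loss is overlap within patients and has nothing to do with efficacy.

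**Break-even in general.** The gap is zero when w on placebo = 1 − (0.80/0.90)(1 − w on 240 mg). For 0%, 5% and 10% on 240 mg this gives 11.1%, 15.6% and 20.0% on placebo. The totals therefore agree only when placebo has about 10 to 11 points more worsening SAEs. That is roughly a threefold ratio at 5% on 240 mg and a twofold ratio at 10%.

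**Other totals, same formula, also assumed rates.**
- Stops for AEs, non-lupus 5% against 15% (true gap +10): +7.4 points with flares of 5% against 2.5%, and 0.0 with 15% against 5% (both totals 19.25%).
- Any AE, non-lupus 60% against 75% (true gap +15): +13.6 points with flares of 5% against 2.5%, and +5.5 with 30% against 10%.

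**The case against.** The strongest reply is that the plan is consistent and the relevant harms remain visible. SAP 7.8.1 plans organ-class and preferred-term tables, a related-AE table, and separate displays for infections, malignancies and lymphoproliferative disorders, thromboembolism, cytokine release, hypersensitivity and liver injury. SAP 7.8 lists individual values, and Protocol 3.1.1 provides a DMC with unblinded data. This stands. A reader might infer that a dose's toxicity could be hidden; the documents do not support that, only dilution of summary counts.

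A reader might also infer that the planned response rates imply more worsening on placebo. They do not. Complete response requires proteinuria below 0.5 g/day with an eGFR condition, and patients enter at 1 g/day or more, so a patient can improve substantially, miss complete response and have no adverse event. The 75/56 ratio above is a scale for illustration only.

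Nor does every flare-driven stop necessarily enter the AE-discontinuation table: SAP 6.6.1 shows lack of efficacy as a separate reason for stopping. The protocol's wording is also that worsening should be recorded, which is weaker than an absolute requirement.

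The shifts are small against sampling error. With 40 per arm and 10% against 20%, the standard error is √(0.10×0.90/40 + 0.20×0.80/40) = 7.9 points, a 95% half-width of about 15.5. No visible rule selects a dose from crude totals. Finally, AE handling follows a sponsor guideline that is cited but not supplied, so a split display there cannot be ruled out.

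These arguments limit the size of the point. They do not remove it: the visible plan offers no patient-level total free of lupus worsening, and the preferred-term rows cannot supply one. Sampling error does not cancel a shift that, if flares are reduced, always goes the same way.

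**Conclusion.** The point holds in limited form. As described, the overall AE, SAE, AE-discontinuation and maximum-grade totals mix lack of efficacy with toxicity, and they understate the non-lupus excess of any dose that reduces flares.

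Under the assumed rates, a true +10-point SAE excess appears as about +8.5 to +3.9 points at the 75/56 ratio. With 5% worsening SAEs on 240 mg it approaches zero or reverses only with about three to four times as much on placebo (15% to 20%). If flares are rarer, at 5% against 2.5%, the loss is about 2.5 points. All of this rests on assumed rates and on independence of the two kinds of event; the true size cannot be derived from the documents.

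Specific toxicities remain visible elsewhere, and sample size, power and alpha are unaffected. It is a worthwhile low-cost improvement to the safety summaries, and the plan is not internally contradictory without it.

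**What to change.** In SAP 7.8.1:

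- Keep all full tables unchanged.
- For overall AEs, SAEs, AEs leading to discontinuation and maximum RCTC grade, add a supplementary presentation excluding worsening of the disease under study.
- Identify these events by the recorded AE type where it is available. SAP 6.6.1 shows that type only in the rules for patients who stop early, so otherwise use a list of lupus preferred terms. Because an unblinded interim is part of the design (Protocol 7.4), blinded staff should fix the list before final unblinding.
- Keep in the supplementary presentation any event that could be drug-related renal toxicity.
- Show lupus worsening on its own line by arm, and state that dose safety is read from both presentations.

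If the sponsor's AE guideline already provides such a display, one sentence in the SAP saying so is enough.

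The cost is SAP wording, one filter and a few tables, with no new data needed in principle. The small downside is dependence on correct classification of lupus events, which retaining the full tables limits.

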5.6 OTHER ASSESSMENTS

5.7 APPROPRIATENESS OF MEASUREMENTS

The measures conducted for primary and secondary endpoints are using standard methods. Measures conducted for exploratory further endpoints might be new methodologies already used in clinical trials in LN but not yet validated for this rare disease.

6. INVESTIGATIONAL PLAN

6.1 VISIT SCHEDULE

For a detailed overview of the trial procedures and time windows for visits, please refer to the [Flow Chart](#).

The trial consists of a screening visit followed by a one year treatment period and 2 follow-up visits.

The study will last until every evaluable entered patient has completed the last follow-up visit.

After giving his/her Informed Consent, the patient will be screened for inclusion and exclusion criteria for the study at visit 1. Visit 2 will be scheduled after visit 1, after results from central laboratory are obtained (a minimum of 7 days to be planned). The screening phase must not be longer than 4 weeks (from visit 1 to visit 2). The patient will be randomised at visit 2 if all inclusion and none of the exclusion criteria are fulfilled.

Windows of ± 1 to ± 5 days is allowed for a majority of visits, to accommodate scheduling problems. If a delay is observed for a particular visit, the original calendar schedule should be kept for subsequent visits (delays should not accumulate). If a visit is missed the patient should be instructed to come for a visit as soon as possible. Investigator should contact the BI monitor to discuss further schedule.

Follow up visits have to be organized at 4 and 8 weeks after End of treatment

6.2 DETAILS OF TRIAL PROCEDURES AT SELECTED VISITS

6.2.1 Screening and run-in period(s)

Screening Period

Written informed consent must be obtained before any protocol specific screening assessments are performed.

The screening visit should take place within 7-28 days prior to randomization (Visit 2). All study procedures and assessments including the repeated tests in determining the patient's eligibility must be available prior to Visit 2.

Patients must satisfy all inclusion and exclusion criteria prior to randomization (Visit 2).

Details of any patient who is screened for the study but is found ineligible must be entered in an enrolment log (see ISF) and documented in the eCRF.

It is allowed to re-test (once) a lab parameter that is found abnormal at visit 1 if it is thought to be a measurement error (i.e. there was no abnormal result of this test in the recent history of the patient and there is no related clinical sign)".

It is allowed to re-test the proteinuria if the result from spot ratio at screening visit does not correspond to recent measurements done at site. In that case it is preferred to do a 24h measurement.

For a detailed description of the trial procedures at the screening visit, refer to [Flow Chart](#).

Baseline Conditions/Medical history:

As a precaution, risk factors for thromboembolic disease (including medical history of DVT/TE) should be specifically checked. If clinically relevant, the case should be discussed with the TCM/TMM prior to randomization. History of antiphospholipid syndrome should be recorded and patients should be excluded from the study.

Pregnancy tests:

Serum pregnancy test will be performed at screening visit. A urine dipstick test will be done during the screening phase and immediately before starting medication. In case of a positive urine pregnancy test result, a blood sample for serum pregnancy test will be drawn for confirmation. Only those females with a negative pregnancy test will start treatment with MMF and will receive study medication.

6.2.2 Treatment period(s)

For details description of trial procedures during the treatment period, refer to [Flow Chart](#). Only additional critical information is listed below.

Eligible patients will be randomised to receive the first dose of study medication at Visit 2. Each patient can only be randomised once in the trial via IRT.

Visit 2, 2.1, 2.2: drug administration:

The induction phase with SOC might have started for some patients already before the randomisation in the trial.

- MMF: if the patient is naïve with MMF or has received a dose < 2g/day, he will start receiving 2-3g/day MMF at visit 2
- Intravenous Glucocorticoids: patients who have not yet received any high dose pulse IV steroids will receive 500 mg methylprednisolone for 3 days (visits 2, 2.1, 2.2). If considered necessary by the investigator, a maximal dose of 1000 mg methylprednisolone for 3 days is acceptable. In case the patient had already received pulse steroids (max 3g total within last 6 weeks) he will receive additional IV steroids only to reach 1.5g total. If the 1.5 g is reached the visit 2.1 and 2.2 are not necessary.

The investigator will prescribe daily oral steroids starting the day after the last IV steroids. Refer to [section 4.2.1](#). This should be tapered down to 10 mg prednisone equivalent within 12 weeks.

drug injection:

For all other weekly injection, this can either be administered on-site or at home by the patient.

Urine collection:

At visit 2 and 11 and 16, 2 times 24h collection of urine will be performed. The patient will be given instructions and material to allow collection of urine during 2 days in the week preceding the visit. At other time points, proteinuria will be assessed by spot urine.

Drug administration:

According to the [Flow Chart](#) the patients will be receiving the syringes necessary for the next week(s) injection at home between two visits. The patients will be given instructions for injection and treatment number, and a diary to record the exact date and time of injection

At any visit, should a decision be made to discontinue the patient from study medication, please complete EOT visit.

